**Table 5. Incidence of AEs by preferred term - n(percent) of patients (Safety analysis set) – Cohort 1 (age 5-11 years)**

Preferred term	-Period1-		-Period					Total
	15mg AFQ056	2- AFQ056	25mg AFQ056	50mg AFQ056	60mg AFQ056	100mg AFQ056		
	N=12 n (%)	N=1 n (%)	N=1 n (%)	N=3 n (%)	N=1 n (%)	N=6 n (%)	N=12 n (%)	
Patients with AE(s)	4(33.3)	1(100)		3(100)	1(100)	4(66.7)	9(75.0)	
Preferred term								
Vomiting			1(100)		2(66.7)		3(50.0)	6(50.0)
Diarrhea		1(8.3)			1(33.3)			2(16.7)
Dizziness						2(33.3)	2(16.7)	
Initial insomnia			1(100)			1(16.7)	2(16.7)	
Psychomotor hyperactivity			1(100)		1(33.3)			2(16.7)
Anticipatory anxiety	1(8.3)					1(16.7)	1(8.3)	
Anxiety					1(100)			1(8.3)
Coordination abnormal						1(16.7)	1(8.3)	

AFQ056 for Language Learning in Children with FXS

Version v15

Version date 02/03/2021

Dyskinesia		1(33.3)		1(8.3)
Eye pain			1(16.7)	1(8.3)
Feeling hot			1(16.7)	1(8.3)
Food poisoning	1(8.3)			1(8.3)
Headache			1(16.7)	1(8.3)
Hordeolum	1(8.3)			1(8.3)
Hot flush			1(16.7)	1(8.3)
Hyperhidrosis			1(16.7)	1(8.3)
Hypersomnia			1(16.7)	1(8.3)
Mydriasis			1(16.7)	1(8.3)
Nasopharyngitis		1(33.3)		1(8.3)
Non-cardiac chest pain			1(16.7)	1(8.3)
Oropharyngeal pain				1(8.3)
Pollakiuria		1(33.3)		1(8.3)
Swelling face			1(16.7)	1(8.3)

Arranged in descending order of frequency by total column.

Source: Table 14.3.1-1.1, Novartis CSR for study CAFQ056B2154

**Table 6. Incidence of AEs by preferred term - n(percent) of patients (Safety analysis set) – Cohort 2 (age 3-4 years)**

Preferred term	-Period1-		-Period				Total
	15mg AFQ056	2- AFQ056	20mg AFQ056	25mg AFQ056	50mg AFQ056	100mg AFQ056	
	N=9 n (%)	N=1 n (%)	N=1 n (%)	N=2 n (%)	N=4 n (%)	N=1 n (%)	
Patients with AE(s)	2(22.2)	1(100)	1(100)		3(75.0)	1(100)	6(66.7)
Preferred term	-	-	-				
Insomnia	-	-	-		2(50.0)		2(22.2)
Gastrointestinal viral infection		1(100)	-				1(11.1)
Infected bites	1(11.1)	-	-				1(11.1)
Initial insomnia	-	-	1(100)				1(11.1)
Nasal congestion	-	-	-			1(100)	1(11.1)
Pharyngitis	1(11.1)	-	-				1(11.1)
Rash	-	-	1(100)				1(11.1)
Somnolence	-	-	-		1(25.0)		1(11.1)
Urticaria	-	-	1(100)				1(11.1)

Arranged in descending order of frequency by total column.

Source: Table 14.3.1-1.1, Novartis CSR for study CAFQ056B2154

### 3 STUDY DESIGN

The trial will use a double-blind placebo-controlled parallel-group flexible-dose forced titration design in which 100 subjects with FXS, age 32 months to 6 years of age will enter a single-blind 4-month placebo lead-in, followed by an 8-month placebo-controlled phase in which they are randomized 1:1 to AFQ056 or placebo followed by an 8 month open label extension phase in which all participants enrolled by June 15, 2019 will be treated with active drug. For participants enrolled after June 15, 2019, the duration of the open label extension will be shorter and will depend upon when the subject is enrolled and what dose of AFQ056 the participant is taking for stable treatment in the open label extension. The total duration of the stable treatment for those

AFQ056 for Language Learning in Children with FXS

Version v15

Version date 02/03/2021

enrolled after June 15, 2019 will range from 6 months to no open label extension, depending on the number of months after June 15, 2019 the subject is enrolled into the study. The flexible dose design will mimic practice, take into account differential responsiveness and the known inter-child variability in drug levels with AFQ056, and allow use of maximum tolerated dose (MTD) which is likely to be most effective.

Participants will be seen for a screening visit during which they will have assessments (to include language, communication, cognitive, adaptive, behavioral measures, CGI, blood for safety labs and biomarkers, U/A, EKG, ERP and eye tracking) and if they meet entry criteria will start a single-blind 4-month placebo lead-in to provide a control group with treatment as usual for the language intervention placebo group. Subjects will be seen for a study visit 2 months into the placebo lead in (-2 months). It should be noted that although 32 month old children can enter the placebo lead-in, these children will be age 3 years before they are randomized and are potentially exposed to drug, thus the age of treatment will remain within the age range that has been studied in the prior pharmacokinetic study with AFQ056.

At the end of 4 months in the placebo lead-in all subjects will have a repeat battery of assessments and be randomized to drug or placebo at an AFQ baseline visit. The initial dose will be 25 mg BID and dose titration will be done every week based on safety report and side effects alone (efficacy will not be a factor in dose titration due to known strong early placebo effects in prior FXS studies). If the subject has no side effects at each call, the dose will be force titrated (mandatory titration if no side effects) to the next level, 50 mg BID, 75 mg BID and 100 mg BID in order. If there is concern for side effects the dose may be left the same for an additional week or reduced. If there are side effects after the first week of treatment, the 25 mg dose will be allowed to be reduced to 12.5 mg BID. Patients who cannot tolerate 12.5 mg BID will be withdrawn from the study. Subjects will be seen for a study visit for a safety check at 1 month from baseline, during the titration period. The dose can be adjusted weekly through week 7 after baseline. This will give extra weeks after the full titration schedule to ensure the final dose chosen is the optimal one for the given patient. After 7 weeks, the dose will be fixed and at the 2 month visit (language intervention baseline visit) all subjects will have the battery of assessments again and will initiate the language intervention, remaining on a stable AFQ056/placebo dose for the next 6 months.

Families will have training for the language intervention at the 2 month visit, and subsequent instruction and monitoring of delivery of the intervention will occur by weekly video conferencing (per institutional policy) with the language therapist for the first 4 months of the intervention (6 months from randomization), and then monthly for the duration of the study.

Study visits will occur at the 3, 4, 6 and 8 month visits (v6 – 9) after implementation of the language intervention (occurs at 2 months).

- At 3 months: only VAS and CGI assessments will be done
- All baseline assessments except the Mullen, PLS-5, and Children's Sleep Habits Questionnaire will be repeated at 4 and 6 months (visits 7 and 8). Auditory ERP and Eye Tracking will only be repeated at 4 months (visit 7) and not at 6 months (visit 8).
- All baseline assessments will be repeated at the 8 month visit (visit 9), in addition to the EKG and blood/urine tests.

At all visits, the following will be done: an interim history, vital signs, weight, height, a physical and neurological exam, adverse event review, suicidality review, dosing diary/compliance review, concomitant medication/therapy review, language intervention monitoring/review, and inclusion/exclusion criteria review will be done.

[figure not shown]
- The 8 month (visit 9) assessments will serve to evaluate whether AFQ056 was able to amplify language and communication progress over 6 months in a language intervention.
- The 4 and 6 month (visits 7 and 8) assessments will allow an evaluation of the trajectory over time of effects of the language intervention and any potential additional drug effect and whether it occurs early or there is a progressive building of the effect(s) over time.
- The 4 month assessment will also allow some data to be collected in the case of families who are not able to sustain the language intervention with the same intensity in the later part of the 6 months as opposed to the early months. It is not expected this will be a frequent problem, however.

The 4 month placebo lead-in will allow for placebo effects to stabilize, and for the group ultimately randomized to placebo, there will be 6 months (4 month placebo lead-in + 2 months of placebo dose titration after randomization) of placebo treatment without the language intervention, which will allow this group to serve as a treatment-as usual/medication placebo control group for the 6 month language intervention placebo group, thus allowing the effects of the language intervention alone in FXS to be quantified.

After 8 month assessments in the placebo-controlled phase (including 6 months of language intervention), all subjects will enter the extension and be treated with active drug according to the same schedule as in the placebo-controlled phase. All subjects will be dosed with 25 mg BID of unblinded AFQ056 upon completion of the 8 month visit, followed by 2 months of flexible dose forced-titration to the MTD of the dose levels available in the protocol (dose adjustments to be done as described above for the placebo-controlled period for the flexible dose forced-titration). This will be followed by a period of stable treatment. The length of stable treatment will be dependent upon how long after June 15, 2019 the participant enrolls and what dose of drug they are receiving in the open label treatment period. The total duration of the stable treatment for those enrolled after June 15, 2019 will range from 6 months to no open label extension, depending on the number of months after June 15, 2019 the subject is enrolled into the study.

Some subjects will have an acute dose decrease if they were on 50-100 mg BID of active drug in the initial phase but experience from the PK study suggests that children can come off AFQ without withdrawal symptoms and the dose decrease and titration in the open label extension are unavoidable to maintain the blind of the study through the completion of the placebo-controlled period by the final participant. Subjects will continue the language intervention through the extension phase. The open-label extension will allow all children a period of active drug exposure to make recruitment feasible, despite the long placebo period. It will also allow an assessment of more long term-effects of the language intervention and its impact on the ERP and eye tracking biomarker outcomes and other developmental and behavioral outcomes, will allow examination of the trajectory of the language intervention going from placebo to drug treatment in a blinded setting, and will furthermore allow additional long-term safety data to be collected on a larger cohort of children exposed to AFQ056. A diagram of the study design is provided below in Figure 2.

Figure 2. Effects of AFQ056 on Language Learning in Young Children with Fragile X Syndrome (FXS) – Protocol Design

AFQ056 for Language Learning in Children with FXS

Version v15

Version date 02/03/2021

## 4 SELECTION AND ENROLLMENT OF SUBJECTS

### 4.1 Inclusion Criteria

1. Age 32 months to 6 years inclusive at Screening (visit 1).
2. Has a documented *FMR1* full mutation.  
\*\*Note\*\* Presence of mosaicism is allowed.
3. DQ<75 calculated from the Mullen Scales of Early Learning at time of screening.
4. Parent or legal guardian is available and able to communicate well with the investigator, comply with study requirements and provide written informed consent.  
\*\*Note\*\* The Parent or legal guardian who will be signing consent form, should be the individual administering the language intervention
5. English is the primary language spoken in the home and the subject's first language is English.
6. Meet criteria indicating evidence of intentional communication based on parent interview via a communication eligibility screening tool at time of screening.  
\*\*Note\*\* On the Eligibility Screening Tool – Communication, the child must have:
  - a. Section 1: Answer of YES; the child uses at least 5 spoken words to label items on a daily basis.  
OR
  - b. Section 2: At least 3 YES answers to items 1-10 if child does not have at least 5 spoken words.
7. Produces 3 or more intentional acts of communication on the structured portion of the Weighted Communication play sample at time of screening.  
\*\*Note\*\* Subjects are permitted to use augmentative communication devices throughout the duration of the study if the device is the subject's primary form of communication and the device has been prescribed for the subject by an SLP.
8. Stable behavioral and other therapy regimen for 30 days prior to screening.  
\*\*Note\*\* Patients will be allowed to continue their standard-of-care therapies throughout the trial but these will not be changed during the placebo lead-in or placebo-controlled portion of the trial, outside of standard changes occurring from school schedules.
9. Stable dosing of all concurrent psychotropic medications except stimulants for at least 60 days prior to screening. Due to the very short half-life of stimulants (specifically methylphenidate and amphetamine variants), a stable regimen of these medications is required for 2 weeks only.  
\*\*Note\*\* Medications impacting GABA, glutamate and/or mGluR5 pathway receptors are exclusionary and not permitted during study participation. Additionally, stimulant regimens may include combinations of short- and long-acting forms and may be taken with different timing or dosing on different days of the week (e.g. Doses may be skipped on weekends or days off school and extra doses may be given some days for therapy sessions later in the day). The intent is to keep the doses and regimen being used at the time of screening consistent during the trial even if there is some variation in how the medication is taken on different days. Use of CBD oil or hemp based substances legal for sale over the internet are allowed provided that the dosing regimen has been consistent for at least 60 days prior to screening and will remain the same throughout the trial.

### 4.2 Exclusion Criteria

1. Use of medications impacting GABA, glutamate and/or mGluR5 pathway receptors or transmission.  
\*\*Note\*\* Treatment with acamprosate, amantadine, budipine, carbetocin, cycloserine, dextromethorphan, felbamate, ketamine, lithium\*, minocycline, memantine, oxytocin,

remacemide, racemic baclofen, riluzole, fycampa, investigational mGluR5 medications, and/or statins are exclusionary.

\*\*Note\*\* Lithium taken as a dietary supplement is permitted if the dose is less than 5mg/day. A 5mg/day dose is the recommended dietary intake level, and is therefore not considered to be therapeutic. Lithium dosage must remain the same throughout the duration of the trial, and documented in the concomitant medication log.

2. Unstable seizure disorder as defined by any seizure in the 6 months prior to the screening visit, and/or any change in anti-convulsant drug dosing in the 60 days prior to screening.  
\*\*Note\*\* Use of levetiracetam and oxcarbazepine are among permitted anticonvulsants.
3. Use of any other investigational drug at the time of enrollment or within 30 days or 5 half-lives (whichever is longer) of the investigational drug prior to screening until end of study visits (or longer if required by local regulations).
4. History of hypersensitivity to AFQ056 or any mGluR antagonist.
5. History or presence of any clinically significant disease of any major system organ class, within the past 2 years prior to screening including but not limited to neurological, cardiovascular, endocrine, metabolic, renal, or gastrointestinal disorders. This does not include typical features of FXS such as psychological symptoms or history of epileptic seizures.
6. Significant acute illness that did not completely resolve at least four weeks prior to the Screening visit.
7. Abnormal laboratory values at screening that are in the opinion of the investigator are clinically significant and may jeopardize the safety of the study subject.
8. Use of (or use within at least 5 half-lives before dosing) concomitant medications that are strong/moderate inhibitors or inducers of CYP1A1/2, CYP2C9/19 or CYP3A4 (see Appendix B).
9. Subjects who are, in the opinion of the investigator, unable to comply with the requirements of the study.
10. Presence of immunodeficiency diseases at the time of screening, based on medical history, including a positive HIV test result.
11. History of a positive Hepatitis B surface antigen (HBsAg) or Hepatitis C result at time of screening.
12. History or presence of suicidal thoughts and/or suicide attempts.

#### **4.3 Subject Withdrawal Criteria**

Any study subject/legal guardian has the right to voluntarily withdraw informed consent and discontinue study participation at any time without providing specific reasons. Subjects may be considered withdrawn if they state an intention to withdraw, fail to return for visits, or become lost to follow-up for any other reason. If premature withdrawal occurs for any reason, the investigator must make every effort to determine the primary reason for a subject's premature withdrawal from the study and record this information on the Study Completion/Termination CRF.

If a subject is withdrawn from the study during the placebo-lead in period or prior to randomization, they will be brought back in for an abbreviated follow-up/termination visit. At this visit, the following will be done:

- Drug accountability (family will be asked to return all drug kits and supplies)
- Adverse Event Review

The above information will need to be entered into the EDC. If this takes place prior to Baseline, please contact the Study Team, and they will provide instructions on how to deem them ineligible to proceed to randomization in the system.

A physical exam, psychiatric exam, vital signs, and any other assessment per PI discretion may be conducted, but is not required to be done or entered into the EDC.

The investigator should discontinue study treatment for a given subject or withdraw the subject from study if he/she believes that continuation would be detrimental to the subject's well-being. If a subject has intolerable side effects on the lowest dose of AFQ056 allowed in the study, 12.5 mg BID, that subject will be discontinued from the study.

Study treatment *must* be discontinued [and the subject withdrawn from the trial] under the following circumstances and according to Investigator discretion:

- Legal guardian withdraws informed consent.
- Serious AE occurs that is in the opinion of the investigator suspected to be related to the study medication.
- Severe CNS-related AE occurs that is in the opinion of the investigator suspected to be related to the study medication.

The subject may be withdrawn from the study, if:

- Clinically significant changes of laboratory parameters and/or vital signs occur that are in the opinion of the investigator suspected to be related to the study medication. The clinical significance of laboratory abnormalities and other abnormal assessments will be assessed and interpreted by the investigator in the context of the overall clinical presentation.
- Subject is lost to follow-up.
- $\geq 7$  consecutive days of study medication are missed or a total of  $\geq 14$  days of study medication are omitted once the subject has begun dosing at any time during the study
- Protocol deviation occurs that in the opinion of the Site PI or Study Team may alter the study results (e.g. administration of concomitant medication).

If a subject withdraws from the study after randomization, a Termination visit should be conducted as soon as possible. The assessments and procedures completed during the termination visit will depend upon whether the subject discontinued study drug prior to the termination visit. Assessments and procedures to be conducted as possible based on agreement of the caregiver at the termination visit(s) as follows:

- The subject is on study drug at the time of the visit
  - The termination visit will include all the assessments and procedures for the 16 month visit (visit 14).
  - If possible, the patient will return for a follow up visit after weaning drug one month after the termination visit and do all the assessments for the 17 month visit (visit 15)
- The subject discontinued study drug prior to the visit
  - The termination visit will include the following safety assessments and procedures as possible
    - AE review
    - Blood draw
    - Urine dipstick
    - EKG
    - Vitals
    - Physical, neurological and psychological exams
    - Suicidality assessment
    - Fundoscopic exam
    - Study drug accountability
- The subject discontinued study drug but had a full battery of tests within the past two months after being on study drug for at least two months

AFQ056 for Language Learning in Children with FXS

Version v15

Version date 02/03/2021

- The termination visit will include all the assessments and procedures for the month 17 visit (visit 15)
- A follow up visit via phone or email after the Termination Visit with the subject off study drug should be conducted approximately 30 days after the termination visit.

Subjects that are withdrawn after randomization will not specifically be replaced as it is expected that there will be less than a 10% withdrawal rate. If the rate exceeds 10% an amendment will be considered to replace subjects.

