Once a subject is randomized and a kit assigned, the parent/caregiver will continue to receive at every 2-month in-person study visit bottles containing 500 mg of active drug or matching placebo powder, as well as bottled water and premarked 60 cc syringes with 50 cc fill line to use for reconstitution of the AFQ056 powder. Subjects will start on 25 mg BID (2.5 cc BID) or matching placebo after randomization and the dose will be titrated weekly depending on tolerability. If the subject has no side effects at each call, the dose will be force titrated to the next level, 50 mg BID, 75 mg BID and 100 mg BID in order. If there is concern for side effects the dose may be left the same for an additional week or reduced. If there are side effects after the first week of treatment, the 25 mg dose will be allowed to be reduced to 12.5 mg BID. See section 9.1 also for dose adjustment considerations. Patients who cannot tolerate 12.5 mg BID will be withdrawn from the study. Subjects will be seen for a study visit for a safety check at 1 month from baseline, during the titration period. The dose can be adjusted weekly through week 7 after baseline. After randomization, monitoring procedures to ensure correct reconstitution

with parent/caregivers will be identical to those described above for the placebo lead-in. Drug accountability/compliance will be assessed at every 2-month in-person visit after Baseline (i.e. when drug is dispensed). Parents/legal guardians should be reminded to bring all study drug bottles with them to each 2-month visit when drug accountability is to be done. For more details, please refer to the Study Medications/Central Pharmacy section of the Manual of Operations.

The following table provides recommendations and guidelines regarding dose titration. Please note the Site Investigators will have the opportunity to contact the Independent Medical Monitor (IMM) should they be unclear as to how to proceed, and need additional input and guidance. Details about how to contact the IMM can be found in the Manual of Operations.

AE Grade/Severity	Relationship	Most Likely Drug Action	Possible Other Drug Actions						
Grade 1 (Mild)									
	Unrelated	Increase							
	Unlikely	Increase							
	Possibly	Increase							
	Probably	Increase	Hold at physician discretion if AE non tolerable for patient/family and/or concern for worsening AE with increase						

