	Definitely	Increase	Hold at physician discretion if AE non tolerable for patient/family and/or concern for worsening AE with increase						
Grade 2 (Moderate)									
	Unrelated	Increase							
	Unlikely	Increase							
	Possibly	Increase	Hold at physician discretion if AE non tolerable for patient/family and/or concern for worsening AE with increase						
	Probably	Hold	Increase at physician discretion if AE considered tolerable, Decrease if AE considered intolerable by family						
	Definitely	Hold	Increase at physician discretion if AE considered tolerable, Decrease if AE considered intolerable by family						
Grade 3 or higher (severe)									
	Unrelated	Increase	Increase at physician discretion, if AE not overly interfering with dose finding						
	Unlikely	Hold	Increase at physician discretion, if AE not overly interfering with dose finding						
	Possibly	Hold							
	Probably	Decrease							
	Definitely	Decrease							

Please note, adverse events will be graded based on CTCAE version 4.0, with the exception of behavioral adverse events, including but not limited to the following behaviors commonly seen in FXS:

- Hyperactivity
- Attention
- Anxiety
- Perseverative behavior
- Irritability/tantrumming/aggressive behavior/self-injury

AFQ056 for Language Learning in Children with FXS

Version v15

Version date 02/03/2021

- Hypersensitivity

The above behaviors will be noted as absent (none), mild, moderate or severe and captured on the Psychiatric/Behavioral exam CRF. If worsening in any one of the above categories is determined to be a clinically significant change from baseline by the treating physician, it would then also be captured as an adverse event and recorded on the AE CRF accordingly. A “clinically significant” change from baseline is defined as behavior that is not just related to a single event or lack of cooperation in certain settings such as the study visit. Rather, the change should be seen consistently. Minor fluctuations in behavior typical to the individual should not be captured as clinically significant.

For the purposes of the behavioral events being followed in this study, the following definitions of mild, moderate and severe will be utilized:

- **Mild:** the behavior may be present in just one domain of functioning and may be confined to one setting, but results in a marginal worsening in quality of life.

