## **8 CRITERIA FOR INTERVENTION DISCONTINUATION**

Discontinuation criteria for individual subjects will be as follows.

AFQ056 for Language Learning in Children with FXS  
Version v15  
Version date 02/03/2021

Study treatment must be discontinued [and the subject withdrawn from the trial] under the following circumstances and according to Investigator discretion:

- The legal guardian withdraws informed consent.
- A serious AE occurs that is in the opinion of the investigator suspected to be related to the study medication.
- A severe CNS-related AE occurs that is in the opinion of the investigator suspected to be related to the study medication.
- A subject has intolerable side effects on the lowest dose of AFQ056 allowed in the study, 12.5 mg BID, that subject will be discontinued from the study.
- The investigator feels continuation in the study would be detrimental to the subject's well-being.

A subject may be withdrawn from the study, if:

- Clinically significant changes of laboratory parameters and/or vital signs occur that are in the opinion of the investigator suspected to be related to the study medication. The clinical significance of laboratory abnormalities and other abnormal assessments will be assessed and interpreted by the investigator in the context of the overall clinical presentation.
- The subject is lost to follow-up and is late for a study visit by over 1 month.
- $\geq 7$  consecutive days of study medication are missed or a total of  $\geq 14$  days of study medication are omitted once the subject has begun dosing between study visits at any time during the study.
- A protocol deviation occurs that in the opinion of the Site PI or Study Team may alter the study results (e.g. administration of concomitant medication).

In cases in which it is unclear if the patient should be withdrawn from the study, the site investigator will discuss the case with the PPI, Study Team and medical monitor if needed, and a decision will be made regarding whether the subject can stay in the study and if so under what conditions. Subjects discontinued from the study after randomization will complete a Termination visit at which they will undergo the procedures listed for the 16 month visit (visit 14) and then a Follow Up visit at which they will undergo the procedures listed for that visit (visit 15). Subjects will not be maintained in follow up activities through the study after completion of the Follow Up visit.

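### During dose titration, the 5.1 table says hold or reduce for severe, drug-suspected CNS events that 4.3 and 8 list for discontinuation, and no text ranks the two

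*Combined protocol and SAP*

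**What the plan says.** Section 4.3 lists circumstances in which study treatment must be discontinued and the child withdrawn. One is "Severe CNS-related AE occurs that is in the opinion of the investigator suspected to be related to the study medication". Section 8 repeats it: "A severe CNS-related AE occurs that is in the opinion of the investigator suspected to be related to the study medication". Both lists open with a clause that leaves room for investigator discretion. For doubtful cases, section 8 adds a route that begins "In cases in which it is unclear if the patient should be withdrawn from the study" and leads to the protocol PI, the Study Team and, if needed, the medical monitor.

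Section 5.1 governs weekly titration and contains a table of dose actions by AE grade and relatedness. Its status is advisory: "The following table provides recommendations and guidelines regarding dose titration". The next sentence lets a site that is unsure contact the Independent Medical Monitor. The only cross-reference nearby on dose adjustment is "See section 9.1 also for dose adjustment considerations". Section 9.1 describes the design and contains no AE-based dose rule.

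Section 6.2.3 allows reductions down to 12.5 mg BID in titration periods, without a CNS exception. It names 4.3 as the place where individual discontinuation criteria are listed.

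On behaviour, 5.1 says that worsening of a listed behaviour becomes an AE when it "is determined to be a clinically significant change from baseline by the treating physician, it would then also be captured as an adverse event", and it defines mild, moderate and severe grades. Section 6.3.14 says that clinically significant new problems, or worsening beyond the child's known pre-enrolment fluctuation, lead to a dose decrease and are recorded as an AE.

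**The concern.** A site titrating a child works from the 5.1 table. If the child has a severe CNS event judged possibly related, the table says to keep the same dose. If it is judged probably or definitely related, the table says to reduce the dose. Sections 4.3 and 8 list that event for discontinuation. Nothing in the table or its introduction tells the site that another rule applies.

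Two things are at stake. The first is safety: 6.3.9 acknowledges that these children cannot spontaneously report all of their side effects, if any, so protection depends on what the site does with what it sees. The second is consistency: for the same event, one site could withdraw the child, who under 6.2.4 is not followed beyond the follow-up visit, while another reduces the dose and continues.

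**Working it through.** This is mainly a comparison of texts. The plan states no figure to reproduce.

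**Step 1. What counts as suspected.** The relatedness scale under 10.4.1.3 labels possibly, probably and definitely related events as suspected reactions. These are the three levels that trigger the rule in 4.3 and 8.

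**Step 2. The severe rows side by side.**

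| Severe CNS event, relatedness | 4.3 and 8 | 5.1 table, Grade 3 or higher | Alternative in the table |
|---|---|---|---|
| Possibly | Discontinue (with discretion) | Hold | none |
| Probably | Discontinue (with discretion) | Decrease | none |
| Definitely | Discontinue (with discretion) | Decrease | none |

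The table has 3 grades × 5 relatedness levels = 15 rows. Discontinuation appears in 0 of 15. Decrease appears in 4 of 15, counting both action columns: 2 at Grade 2 (as an alternative) and 2 at Grade 3 or higher. All 3 of the severe, suspected rows differ from 4.3 and 8 when the event is CNS-related.

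**Step 3. When the table applies.** Titration runs from baseline to month 2 and again from month 8 to month 10, with adjustments allowed through week 7 of each window. In the blinded fixed-dose phase (months 2 to 8), sections 6.2.3 and 7 already require withdrawal if a dose reduction is needed for side effects. The conflict therefore falls mainly in the two titration windows.

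**Step 4. How often.** The documents give no rate for severe CNS events in this age group. The exact two-sided 95% upper limit for 0 events in n is 1 − 0.025^(1/n).

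- Paediatric PK study (2.2): 0 of 21, all AEs mild. 1 − 0.025^(1/21) = 16.1%.
- Adults and adolescents on AFQ056 (Table 4): 75 + 69 + 84 = 228. If the statement in 2.2 that side effects were mild to moderate covers all of them, 0 of 228 gives 1 − 0.025^(1/228) = 1.6%.

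Applied to 50 children randomised to AFQ056, on the assumption of similar rates, these limits correspond to 50 × 0.161 ≈ 8 and 50 × 0.016 = 0.8 children. They are upper limits, not expected counts; the observed number is zero in both sources.

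**Step 5. The 6.3.14 sentence.** Take a listed behaviour that worsens to a clinically significant but mild degree, beyond known fluctuation. Section 6.3.14 gives a decrease. The table gives Increase in all 5 Grade 1 rows. The only alternative, for probably and definitely related, is "Hold at physician discretion if AE non tolerable for patient/family and/or concern for worsening AE with increase". Decrease is not listed at Grade 1.

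**The case against.** The strongest reply is that this is a missing cross-reference rather than a contradiction. Sections 4.3 and 8 give a specific rule worded as mandatory, the table is general and advisory, and on ordinary reading the specific rule governs. Section 6.2.3 points to 4.3. The table also omits suspected serious AEs, which 4.3 and 8 list too, so it may be meant only for children who continue. Sites can consult the Independent Medical Monitor, and 6.3.14 refers titration detail to the Manual of Operations, which is not among these documents.

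Most of this stands, and it lowers the weight of the point. It does not remove it. Both consultation routes depend on the site recognising that the case is unclear, whereas the table gives a definite action with no alternative in the three rows concerned. Precedence can be inferred but is not stated.

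A reader might go further and infer that the protocol makes withdrawal unconditional and that the table flatly contradicts it. The discretion clause and the table's advisory status do not support that. Nor does the clause make the whole list optional, since guardian withdrawal of consent is on the same list. Grading dose actions by severity is not in itself a conflict.

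On 6.3.14, the paragraph opens by making titration depend on the side effects and their severity. The sentence is therefore better read as loose drafting that does not fit the table's Grade 1 default than as a second rule of equal weight.

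**Conclusion.** The point holds for severe CNS-related AEs suspected to be drug-related that arise during titration. In all three applicable rows, the table's action keeps the child on drug, while 4.3 and 8 list the event for discontinuation, subject to discretion. No text in these documents ranks the two. This rests on reading suspected as the three levels so labelled in 10.4.1.3, and on the Manual of Operations not having settled the matter.

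The events are expected to be rare, so few children would be affected. A reader might take the figure of about 8 as a forecast, but it is an upper confidence limit from 21 children dosed for about a week. A reader might also infer an effect on dropout or power; the documents give no basis for one, and none is claimed.

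The 6.3.14 mismatch is real but minor.

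**What to change.** 1. In the Grade 3 or higher rows for possibly, probably and definitely related, add an entry that CNS-related events are discontinued per 4.3 and 8.
2. Under the table, state that 4.3 and 8 override the table and the dose-reduction text in 6.2.3 and 6.3.14. Add 4.3 and 8 to the cross-reference that now names only 9.1.
3. Say whether behavioural AEs that are severe by the 5.1 definition count as CNS-related.
4. If the sponsor intends dose reduction for such events during titration, amend 4.3 and 8 to say so instead of making changes 1 and 2.
5. For 6.3.14, choose one rule for clinically significant worsening and state it in both places.

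The cost of items 1 to 3 is a few words in three rows, one sentence, one cross-reference, one definition and a site training note. A few children with severe suspected CNS events would be withdrawn rather than dose-reduced, as 4.3 and 8 already state. Sample size and blinding do not change.

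Item 5 is not free. Deferring to the table is the less cautious choice: it removes the stated decrease for clinically significant worsening and so changes Grade 1 and 2 dosing. Adopting the 6.3.14 decrease would instead leave some children at lower doses than forced titration under the table would reach. The sponsor should give its reason for the choice.
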